9.5 Evaluability for Toxicity

All patients who either (1) receive at least 85% of the required dose of larotrectinib according to protocol guidelines in any cycle of treatment or (2) experience a toxicity at least possibly related to the study regimen will be considered in the evaluation of toxicity.

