1.2 Secondary Aims

- 1.2.1 To determine event-free survival (EFS), overall survival (OS), and duration of response (DoR) of children with IFS treated with neoadjuvant larotrectinib prior to local control.
- 1.2.2 To determine the ORR, EFS, OS, and DoR of children with newly diagnosed TRK fusion solid tumors other than IFS treated with neoadjuvant larotrectinib prior to local control.
- 1.2.3 To describe the toxicity of larotrectinib in children with solid tumors and acute leukemia.
- 1.2.4 To determine the percentage of patients with TRK fusion solid tumors with detectable circulating tumor DNA at baseline and after 2 weeks, 4 weeks, 24 weeks of treatment, at the time of discontinuation of larotrectinib therapy, and at progression.

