9.3 Methods of Analysis

Response criteria are described in [Section 10.2](#). A responder is defined as a patient who achieves a best response (as defined in [Section 10.3.4](#)) of PR or CR on the study. Response rates will be calculated as the percent of evaluable patients who are responders, and confidence intervals will be constructed accounting for the two-stage design.

Toxicity tables will be constructed to summarize the observed incidence by type of toxicity and grade. A patient will be counted only once for a given toxicity for the worst grade of that toxicity reported for that patient. Toxicity information recorded will include the type, severity, time of onset, time of resolution, and the attribution(s) to the study regimen.

Time-to-event analyses (time to progression, progression-free survival, overall survival, and duration of response) will be computed one year after the last enrollment in a stratum. Duration of response will be defined among patients with a confirmed best response of either PR and CR, and will be defined as the time from the first observation of either PR or CR until either the first observation of PD (event) or last known observation of the patient (censored observation).

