9.3.1 Adverse Event Monitoring Rule

We will use a Bayesian rule to monitor for protocol-specific toxicities (list given below). We will assume a beta prior distribution with $\alpha = 0.52$ and $\beta = 2.08$. At least once per month, we will calculate the posterior probability (given the data) that the probability of protocol-specific toxicity exceeds the 20% threshold:

$$P(p_{\text{protocol-specified toxicities}} > 20\% \mid \text{Data}) = \int_{0.2}^1 \frac{\binom{n}{x} p^x (1-p)^{n-x} \frac{\Gamma(2.6)}{\Gamma(0.52)\Gamma(2.08)} p^{-0.48} (1-p)^{1.08}}{\int_0^1 \binom{n}{x} q^x (1-q)^{n-x} \frac{\Gamma(2.6)}{\Gamma(0.52)\Gamma(2.08)} q^{-0.48} (1-q)^{1.08} dq} dp$$

Here n is the number of protocol-specific toxicity-evaluable cycles and x is the number of such cycles on which a protocol-specific toxicity event is observed. If there is strong evidence (posterior probability of at least 70% with at least 2 observed toxicities) that there is a per course protocol-specific toxicity probability

of more than 20%, such information will be presented to the DSMC. Examples of situations in which this rule will indicate protocol-specific toxicities have been noted and are presented below:

| Number of failures | Number of patient-cycles |
|--------------------|--------------------------|
| 2 | 6 |
| 3 | 10 |
| 4 | 14 |
| 5 | 19 |
| 6 | 23 |
| 7 | 28 |
| 8 | 32 |
| 9 | 37 |
| 10 | 41 |
| 11 | 46 |
| 12 | 51 |
| 13 | 55 |
| 14 | 60 |

Protocol-specific toxicities of interest include CTCAE v5 Grade 3 or higher fatigue, ataxia, dizziness, ALT increase, AST increase, neutropenia, thrombocytopenia, nausea, and vomiting. For the purpose of this toxicity monitoring rule, patients with leukemia or solid tumors with bone marrow metastases are not evaluable for hematologic toxicities (neutropenia or thrombocytopenia) unless these persist for greater than 14 days after a bone marrow is negative for malignancy and the patient does not have evidence of recurrent disease.

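### For the few treated patients who never reach 85% of the dose in any cycle, Section 9.5 makes entry to the toxicity denominator depend on the outcome and its attribution

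*Combined protocol and SAP*

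**What the plan says.** Section 9.5 (Evaluability for Toxicity) gives two alternative routes into the analysis. The first is by exposure: patients who "receive at least 85% of the required dose of larotrectinib according to protocol guidelines in any cycle of treatment". The second is by outcome: patients who "experience a toxicity at least possibly related to the study regimen will be considered in the evaluation of toxicity". No other route is given, and Section 9 defines no separate safety population of all treated patients.

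The set serves secondary aim 1.2.3: "To describe the toxicity of larotrectinib in children with solid tumors and acute leukemia". Section 9.3 describes the output: "Toxicity tables will be constructed to summarize the observed incidence by type of toxicity and grade". The same section says that the recorded information will include "time of onset, time of resolution, and the attribution(s) to the study regimen", so attribution is available as a reporting variable.

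The monitoring rule in Section 9.3.1 works on cycles, where "n is the number of protocol-specific toxicity-evaluable cycles". Apart from an exception for hematologic toxicities in patients with marrow disease, it does not say what makes a cycle evaluable, and it does not cite Section 9.5.

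**The concern.** A denominator should be fixed by exposure, before anyone looks at what happened. Here, for patients who fail the 85% route, membership is decided by whether the event being counted occurred and by the investigator's view of its cause. The resulting rate is neither an all-treated rate nor a per-protocol rate.

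Two errors follow, and they can run in opposite directions. Every related toxicity is retained while some event-free patients are removed, so related rates are too high. Severe events judged unlikely or unrelated are removed with the patient if no related toxicity accompanies them, so an all-cause rate can be too low. Early stoppers are few, but they are of particular interest in a safety table.

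The contrast with Section 9.4 shows the oddity. Response evaluability starts from one dose and includes death on protocol therapy. A child who died early in Cycle 1 of an event judged unrelated, with no related toxicity, would count as a non-responder and be absent from the toxicity evaluation.

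**Working it through.** **1. The plan's own figures.** Section 9.5 states no rate to reproduce. The one stated toxicity calculation with an evaluable denominator is the monitoring boundary in Section 9.3.1: prior Beta(0.52, 2.08), mean 0.52/2.60 = 0.20, with a signal at a "posterior probability of at least 70% with at least 2 observed toxicities". Taking, for each count x, the largest n for which the Beta(0.52 + x, 2.08 + n − x) posterior gives P(p > 0.20) ≥ 0.70 reproduces all 13 rows. For example, 2/6 gives 0.7001 and 14/60 gives 0.7135. The table is correct; the open question is what feeds n.

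**2. Who fails the exposure route.** Dosing is twice daily for 28 days (Section 4.1), so 56 doses per cycle, and 0.85 × 56 = 47.6. A patient who takes every dose and stops after Day 23 has 46/56 = 82.1% and fails. One who stops after Day 24 has 48/56 = 85.7% and passes. One adequate cycle out of up to 26 is enough.

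**3. Related toxicity.** Let u be the share of treated patients below 85% in every cycle and p the related-toxicity rate, taken as equal in both groups. All events stay and u(1 − p) of patients leave, so

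reported rate = p / [(1 − u) + u·p].

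Both u and p are assumed; the documents give neither.

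| u | p = 10% reported as | p = 20% reported as | expected exclusions at p = 20%, N = 21 | same, N = 70 |
|---|---|---|---|---|
| 5% | 10.5% | 0.20/0.96 = 20.8% | 0.8 | 2.8 |
| 10% | 11.0% | 0.20/0.92 = 21.7% | 1.7 | 5.6 |
| 20% | 12.2% | 0.20/0.84 = 23.8% | 3.4 | 11.2 |

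Exclusions are N·u·(1 − p). N = 21 is the full size of one two-stage cohort (Section 9.2) and 70 is the maximum enrollment (Section 9.1). In counts, 4 patients with a related event among 21 treated, with 2 event-free patients excluded, gives 4/19 = 21.1% against 4/21 = 19.0%.

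**4. Severe events judged unrelated.** The excluded patient leaves the denominator too, so k/N becomes (k − 1)/(N − 1), a fall of (N − k)/[N(N − 1)].

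- N = 21, k = 4: 4/21 = 19.0% becomes 3/20 = 15.0%, a fall of 17/420 = 4.0 points.
- N = 70, k = 14: 14/70 = 20.0% becomes 13/69 = 18.8%, a fall of 56/4830 = 1.2 points. With k = 1 the fall is 69/4830 = 1.4 points.

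As a rate, assume u = 10%, a severe unrelated event in 30% of under-dosed and 10% of other patients, and an independent 20% related-toxicity rate. The true rate is 0.9 × 0.10 + 0.1 × 0.30 = 12.0%. The reported rate is (0.09 + 0.1 × 0.2 × 0.30)/0.92 = 10.4%, and 0.024/0.12 = 20% of these events are lost. If the event is equally frequent (10%) in both groups, the rate stays at 10%, but 8% of the events still disappear. The downward bias therefore needs the excluded patients to have more such events than those retained.

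**5. Monitoring, only if evaluable cycles inherit Section 9.5.** One event-free cycle can decide a signal: 3/10 gives 0.715 (signal) and 3/11 gives 0.660 (none); 2/6 gives 0.700 and 2/7 gives 0.632.

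**The case against.** The strongest reply is that almost nobody is affected and nothing is decided on these rates. Much of this stands.

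- A reader might infer that under-dosed patients in general are excluded. The text does not support that: a poor Cycle 1 followed by one adequate cycle admits the patient. The required dose can also be read as the dose after protocol-directed reduction, which would narrow the group further, although Section 9.5 does not say so.
- A reader might infer that severe events judged unrelated are generally dropped. They are not. Anyone admitted by either route has all events tabulated, and the second route has no grade floor. Loss requires three things together: never 85%, no related toxicity, and a severe event judged unlikely or unrelated.
- A reader might reckon each lost event at 1/21 = 4.8 points. That holds the denominator at 21, whereas the patient leaves it; in the 4/21 example the fall is 4.0 points. The aim covers all cohorts, so 70 is at least as relevant a base.
- A reader might infer that safety oversight is compromised. Section 11.8 requires serious events to be reported whether or not related, Section 11.11 collects Grade 3 and higher events without regard to attribution, and the monitoring committee reviews toxicity (Section 12.2). The monitoring rule does not cite Section 9.5.
- Prior data suggest a small group. In the pediatric phase 1 trial (Section 2.4.1), 1 of 24 patients stopped for an adverse event, a dose-limiting ALT elevation that the second route would have counted.

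These points limit the size. They do not remove the defect: stopping in Cycle 1 can also follow progression, refusal, physician decision or non-compliance (Section 8.1), which is plausible in the relapsed leukemia cohort, and the wording still selects such patients by outcome.

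**Conclusion.** The point holds as a minor defect in the definition of an analysis set. It touches a descriptive secondary aim, not the response endpoint or the collection of safety data.

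The upward direction for related toxicity follows from the wording alone whenever some patients are under-dosed throughout and not all of them have a related toxicity. The size does not: it rests on an assumed 5% to 20% under-dosed share and on an equal toxicity rate in both groups. The all-cause direction is conditional on severe unrelated events being more frequent among the excluded than among those kept. An effect on the monitoring rule is an open question of definition and not a demonstrated error.

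**What to change.** In Section 9.5, define the toxicity population as all patients who received at least one dose of larotrectinib. In Section 9.3, tabulate all-cause events and at-least-possibly-related events separately on that population. Keep the 85% set only as a sensitivity analysis, stating whether the required dose means the full dose or the dose after protocol-directed modification. In Section 9.3.1, define a toxicity-evaluable cycle without reference to whether an event occurred.

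The cost is one extra set of tables and slightly changed rates. The data exist for Grade 3 and higher events and for events needing expedited reporting (Section 11.11); full all-cause tables of lower grades may not be possible. Accrual is complete and results have been reported (Section 2.7.1), so the change would apply to remaining reports during the five-year follow-up and should be labeled as made after the first results. A count of treated patients excluded under the current rule would show at once whether the issue has any practical size.

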9.6 Sex and Minority Accrual Estimates

The sex and minority distribution of the study population is expected to be:

| Racial Categories | DOMESTIC PLANNED ENROLLMENT REPORT | | | | Total | |
|---|------------------------------------|--------------------|--------|------|-------|--|
| | Ethnic Categories | | | | | |
| | Not Hispanic or Latino | Hispanic or Latino | Female | Male | | |
| American Indian/ Alaska Native | | | | | | |
| Asian | | | | | | |
| Native Hawaiian or Other Pacific Islander | | | | | | |
| Black or African American | 8 | 6 | | | 14 | |
| White | 13 | 19 | 9 | 10 | 51 | |
| More Than One Race | | | | | | |
| Total | 21 | 25 | 9 | 10 | 65 | |

| Racial Categories | INTERNATIONAL (including Canadian participants) PLANNED ENROLLMENT REPORT | | | | Total | |
|---|---|--------------------|--------|------|-------|--|
| | Ethnic Categories | | | | | |
| | Not Hispanic or Latino | Hispanic or Latino | Female | Male | | |
| American Indian/ Alaska Native | | | | | | |
| Asian | | | | | | |
| Native Hawaiian or Other Pacific Islander | | | | | | |
| Black or African American | | | | | | |
| White | 2 | 3 | | | 5 | |
| More Than One Race | | | | | | |
| Total | 2 | 3 | | | 5 | |

This distribution was derived from all patients enrolled on prior COG DVL Phase 2 trials.

9.7 Analysis of CSF to Plasma Larotrectinib Concentrations

Larotrectinib concentration in plasma and CSF will be quantified by a validated LC-MS assay for patients with leukemia who have sampling while on study. The ratio of non-protein bound larotrectinib concentration in the plasma and CSF will be calculated. These ratios will be summarized with simple summary statistics, including means, medians, ranges, and standard deviations (if numbers and distribution permit).

9.8 Analysis of Biological and Correlative Endpoints

9.8.1 Histology and Immunohistochemistry

A descriptive review of tumor histology will be performed. This will include central review of all cases at the time of diagnosis. The pattern of immunohistochemical staining with a pan-TRK antibody will be correlated with fusion type, to evaluate use as a surrogate marker of fusion status and better define the patterns of expression as they relate to individual fusion partners and amongst various tumor types. Post-therapy specimens will be reviewed to document patterns of tumor response to therapy and provide centralized review of margin status where applicable. When possible pan-TRK immunohistochemistry will be performed to aid in evaluation of the infiltrative border of the tumor and to confirm the persistence of pan-TRK protein expression in the setting of neoadjuvant larotrectinib.

9.8.2 Central Confirmation of TRK Fusions by Next Generation Sequencing

Anchored multiplex PCR (AMP) is a method for detecting gene rearrangements without prior knowledge of fusion partners (2). Double-stranded cDNA is end-repaired, adenylated, and ligated to universal half functional adapters. Two rounds of nested low-cycle PCR then enriches targets and renders the adapters on the enriched targets functional for sequencing. The assay assesses nucleic acid sequences with a target-specific nested primer on one side, and a universal adapter on the other, such that a priori knowledge of one fusion partner is needed. The assay used in this study includes target-specific primers for all three NTRK genes and thus can detect TRK fusions with both known and novel 5' fusion partners. The method is effective with low nucleic acid input from formalin fixed paraffin-embedded specimens.

VALIDATION: Validation will be completed by December 2018. Thus far we have run over 100 cases, including 60 unique fusion-positive samples. 100% of samples successfully completed library preparation with acceptable QC metrics, including samples derived from both FFPE (5 unstained slides per case) and fresh/frozen tissue as well as samples across a range of nucleic acid input (down to 10 ng of total nucleic acid). So far, fusions have been correctly identified in over 95% of cases. A detailed report will be available when validation is complete.

SPECIFIC QUALITY CONTROL AND QUALITY ASSURANCE PARAMETERS TO DETERMINE SATISFACTORY PERFORMANCE OF THE BIOINFORMATICS PIPELINE:

1. Percentage of nucleated cells that are tumor cells
2. Nucleic acid concentration
3. Library nucleic acid quantification
4. Cluster density
5. Percentage of bases higher than the minimum Phred score (Q30) of all bases called
6. Demultiplexing success
7. Percentage of reads passing a minimum Phred score (Q30)

8. Mean on-target coverage of reads
9. AT/GC mapping bias
10. Depth of coverage
11. Observed sex matches reported sex
12. Specific version of bioinformatics pipeline
13. Integrity of data files during transfer between systems (sequencer to pipeline; pipeline to knowledge database) using a hash/checksum method

9.8.3 Circulating tumor DNA

A combination of hybrid-capture next-generation sequencing (NGS) and digital droplet PCR (ddPCR) will be used to detect and quantify circulating tumor DNA (ctDNA) in blood samples obtained from patients enrolled on this study. NGS will be performed using capture probes targeting the genomic introns involved in NTRK gene fusions and the coding regions of the three NTRK genes. Our assay was designed using the SureSelect Advanced Design Wizard (Agilent Technologies). Normalized and pooled barcoded sequencing libraries are enriched using the SureSelectXT Fast Target Enrichment System (Agilent Technologies) with this bait set. Post-enrichment captures are sequenced with an intended coverage at target regions of 500X. Identification of targeted translocations are detected using BreakKmer.⁴⁹ To quantify the number of translocations and wild-type reads detected in each sample, a custom algorithm designed to realign all sequencing reads to either the reference human genome or the patient-specific translocation positive reference sequence (obtained from tumor sequencing) will be used (https://github.com/vanallenlab/peds_ctDNA).⁴⁰ The algorithm will report the number of reads aligned at the patient-specific translocation breakpoint and the number of wild-type reads at the equivalent genomic base-pair location within the human reference genome. Because each cancer genome contains one translocated and one wild-type allele, whereas germline genomes contain two wild-type alleles, we used the following formula to calculate the percentage of ctDNA, where T equals the number of translocation reads and W equals the number of wild-type reads:

$$\% \text{ ctDNA} = \frac{T}{\frac{W-T}{2} + T}$$

ddPCR will be performed using PCR primers designed with Primer3Plus (<http://www.bioinformatics.nl/cgi-bin/primer3plus/primer3plus.cgi>) to amplify patient-specific translocations identified from tumor DNA sequencing. Sample specific primer pairs will be validated with tumor DNA or synthetic DNA as a positive control (Integrated DNA Technologies) and an unrelated human cell line DNA as a negative control. Primers for the housekeeping gene RPP30 designed by Bio-Rad will be used as a reference gene. ddPCR will be performed with 5 ng of pre-capture sequencing libraries for all samples using QX200 EvaGreen SuperMix and the QX200 Droplet Digital PCR system (Bio-Rad). Analysis will be performed using the QuantaSoft program (Bio-Rad). Samples will be performed in duplicate. For each replicate, translocation-positive droplets will be divided by half of the average number of RPP30-positive droplets for that sample and then averaged.

The percentage of ctDNA and frequency with which patients have detectable ctDNA prior to the start of therapy and at times during therapy when subsequent serial samples are obtained will be summarized with simple summary statistics, including means, medians, ranges, and standard deviations (if numbers and distribution permit). In cases of treatment resistance, we will also perform exploratory deep sequencing of ctDNA to determine whether this method can detect the emergence of resistance mutations.

VALIDATION: The above hybrid capture technique has been used to successfully detect NTRK-rearrangements in tumor biopsy samples validating that the assay is a technical success. A similar strategy has also been successfully used to detect translocations in the blood of patients Ewing sarcoma. The hybrid-capture approach is able to detect these translocations when the circulating tumor DNA makes up as little as 1% of the total cell-free DNA extracted from a plasma sample.⁴⁰ Similarly, ddPCR has been used to detect Ewing translocations in the plasma of patients and is sensitive when circulating tumor DNA makes up as little as 0.01% of the cell-free DNA extracted from plasmas.⁵⁰ Furthermore, detection of larotrectinib resistance mutations in ctDNA has been shown in the first two patients to develop acquired resistance on the industry sponsored clinical trials of larotrectinib, demonstrating feasibility of this strategy.^{39, 40}

9.8.4 Neurocognitive Outcomes

Neurocognitive functions will be analyzed using linear mixed-effects models with exponential covariance measures between observations within each patient. Measures to be analyzed will be the ABAS-III (General Adaptive Composite), BRIEF-P or BRIEF-2 (Global Executive Composite Score), the BASC-3 (Internalizing, Externalizing and Behavioral Symptoms Indices) and Peds QL Total Score (see [Appendix XI](#)).

10.0 EVALUATION CRITERIA

10.1 Common Terminology Criteria for Adverse Events (CTCAE)

This study will utilize the CTCAE of the National Cancer Institute (NCI) for toxicity and performance reporting. The descriptions and grading scales found in the revised CTCAE version 5.0 will be utilized for reporting. All appropriate treatment areas should have access to a copy of the CTCAE version 5.0, which can be downloaded from the CTEP web site (http://ctep.cancer.gov/protocolDevelopment/electronic_applications/ctc.htm).

Additionally, toxicities are to be reported on the appropriate case report forms.

Please note: ‘CTCAE v5.0’ is understood to represent the most current version of CTCAE v5.0 as referenced on the CTEP website (i.e., v5.02 and all subsequent iterations prior to version 6.0).

10.2 Response Criteria

As outlined, patients will be assigned to one of the following categories for assessment of response: a) solid tumor and measurable disease ([Section 10.3](#), [Section 10.4](#), and [Section 10.5](#)); b) AML ([Section 10.6](#)); c) ALL ([Section 10.7](#)). Note: Neuroblastoma patients who do not have MIBG positive lesions or bone marrow involvement should be assessed for response as solid tumor patients with measurable or evaluable disease.

